### **5.8.1 Treatment after Initial Radiologic Progression**

If radiologic imaging shows progressive disease (PD), tumor assessment may be repeated  $\geq 4$  weeks later in order to confirm PD with the option of continuing treatment while awaiting radiologic confirmation of progression. If repeat imaging shows a reduction in the tumor burden compared to the initial scan demonstrating PD, treatment may be continued as per treatment calendar. If repeat imaging confirms progressive disease, subjects will be discontinued from study therapy. In determining whether or not the tumor burden has increased or decreased, investigators should consider all target lesions as well as non-target lesions, with the exception of radiated lesions, which will only be considered when evaluating increased tumor burden. The decision to continue study treatment after the first evidence of disease progression is at the Investigator's discretion and will be based on the clinical status of the subject. Subjects may receive study treatment while waiting for confirmation of PD if they are clinically stable as defined by the following criteria:

- Absence of signs and symptoms (including worsening of laboratory values) indicating disease progression
- No decline in ECOG performance status
- Absence of rapid progression of disease
- Absence of progressive tumor at critical anatomical sites (e.g., cord compression) requiring urgent alternative medical intervention

Subjects that are deemed clinically unstable are not required to have repeat imaging for confirmation.

### **5.8.2 Discontinuation of Study Therapy after CR after Cycle 4**

Discontinuation of treatment may be considered for subjects who have attained a confirmed CR that have been treated for at least 10 weeks with pembrolizumab and had at least two treatments with pembrolizumab beyond the date when the initial CR was declared. Subjects who then experience radiographic disease progression may be eligible for up to one year of additional treatment with pembrolizumab via the Second Course Phase at the discretion of the investigator if no cancer treatment was administered since the last dose of pembrolizumab, the subject meets the safety parameters listed in the Inclusion/Exclusion criteria, and the trial is open. Subjects will resume therapy at the same dose and schedule at the time of initial discontinuation. Additional details are provided in [Section 7.1.6.5](#).

### **5.8.3 Treatment with pembrolizumab after SD or PR**

Treatment with pembrolizumab for subjects who have attained a SD or PR should continue every 3 weeks until the subject reaches a confirmed disease progression, achieves confirmed CR as per [Section 5.8.2](#) or experiences an adverse event meeting criteria for discontinuation as per [Section 5.8](#). For patients with long term stable disease or long term PR not meeting CR criteria, a subject may continue treatment for up to 2 years. Subjects experiencing SD or PR may elect to discontinue pembrolizumab treatment any time. Subjects who then experience radiographic disease progression may be eligible for up to one year of additional treatment with pembrolizumab via the Second Course Phase at the discretion of the investigator if no cancer treatment was administered since the last dose of pembrolizumab, the subject meets the safety parameters listed in the Inclusion/Exclusion criteria, and

**Product:** Pembrolizumab

**Protocol/Amendment No.:** UVA Breast 48

V04-13-21

the trial is open. Subjects will resume therapy at the same dose and schedule at the time of initial discontinuation. Additional details are provided in [Section 7.1.6.5.](#)

## **5.9 Subject Replacement Strategy**

### **5.9.1 Replacement of Study Participants**

A participant who is enrolled but who does not receive study drug or any of the study related procedures may be replaced. Every attempt will be made to evaluate any data from these participants for endpoint assessment.

## **5.10 Clinical Criteria for Early Trial Termination**

Early trial termination will be the result of the criteria specified below:

- Quality or quantity of data recording is inaccurate or incomplete
- Poor adherence to protocol and regulatory requirements
- Incidence or severity of adverse drug reaction in this or other studies indicates a potential health hazard to subjects
- Plans to modify or discontinue the development of the study drug

In the event of Merck decision to no longer supply study drug, ample notification will be provided so that appropriate adjustments to subject treatment can be made.

**Product:** Pembrolizumab

**Protocol/Amendment No.:** UVA Breast 48

V04-13-21

## 6.0 TRIAL FLOW CHART

### 6.1 Study Flow Chart

#### ARM A

Trial Period:		Treatment Cycles a										End of Treatment	Post-Treatment		
		Cycle 1		2	3	4	May be repeated beyond 8 cycles					Safety Follow-up-30 days post discon	Follow-Up Every 12 weeks up to 2yrs i	Survival Follow-Up n Annually	
Treatment Cycle:	Main Study Screening (Visit 1)	C1D 1	C1D 15				5	6	7	8					
		1	15	22	43	64	85	106	127	148	Discon h				
Scheduling Window (Days):	see footnotes	± 3	± 3	± 3	± 3	± 3	± 3	± 3	± 3	± 3	At time of Discon	± 3	±3wks		
Informed Consent	X														
Inclusion/Exclusion Criteria	X														
Demographics and Medical History	X														
Prior and Concomitant Medication Review	X	X		X	X	X	X	X	X	X	X	X			
Ultrasound	X														
Focused Ultrasound Treatment			X												
Pembrolizumab Infusion				X	X	X	X	X	X	X					
Post-study anticancer therapy status												X	X	X	
Survival Status														X	
Review Adverse Events		X	X	X	X	X	X	X	X	X	X	X j	X j		
Full Physical Examination	X b														
Pain Assessment (VAS Scale)			X	X											
Directed Physical Examination		X		X	X	X	X	X	X	X	X	X	X		
Vital Signs and Weight	X c	X		X	X	X	X	X	X	X	X	X	X		
ECOG Performance Status	X b	X		X	X	X	X	X	X	X	X				
Pregnancy Test – Urine or Serum β-HCG	X		X	X f											
PT/INR and aPTT	X b			X	X	X	X				X				
CBC with Differential	X b	X		X	X	X	X	X	X	X	X	X	X		

**Product:** Pembrolizumab

**Protocol/Amendment No.:** UVA Breast 48

V04-13-21

Trial Period:		Treatment Cycles a										End of Treatment	Post-Treatment		
		Cycle 1		2	3	4	May be repeated beyond 8 cycles					Safety Follow-up-30 days post discon	Follow-Up Every 12 weeks up to 2yrs i	Survival Follow-Up n Annually	
Treatment Cycle:	Main Study Screening	C1D 1	C1D 15				5	6	7	8					
Days:	Days:	1	15	22	43	64	85	106	127	148	Discon h				
Scheduling Window (Days):	see footnotes	± 3	± 3	± 3	± 3	± 3	± 3	± 3	± 3	± 3	At time of Discon	± 3	± 3wks		
Comprehensive Serum Chemistry Panel b	X b	X		X	X	X	X	X	X	X	X	X			
Urinalysis		X			X		X		X						
T3, FT4 and TSH		X		X		X		X		X					
HIV/Hep C d	X														
Tumor Imaging - CT(or MRI) chest/abdomen/pelvis head when indicated	X g					X g					X g	X			
Symptom Diary		X		X	X	X	X	X	X	X	X	X			
Breast tumor biopsy m		X		X											
Optional tumor biopsies						X k									
Correlative Studies Blood Collection l		X		X	X	X									

a Cycles are 21 days

b Pre-study, within 10 days of registration.

c Pre-study, within 2 weeks of registration.

d HIV/Hep C testing required if known or suspected history or exposure

f Must be completed within 72 hours prior to receiving the first dose of study drug.

g Baseline tumor imaging should be within 28 days of registration. Tumor imaging is planned for within 4 days of receipt of study drug on cycle #4. Imaging is to be every 12 weeks (± 1 week) for any patients continuing on therapy beyond cycle #4.

h If a subject is discontinued and the assessments have been completed as part of another study visit, the assessments do not need to be repeated. Tumor imaging does not need to be repeated if scans have been completed within the past 8 weeks.

i Follow-up visits may be discontinued at (1) the start of new anti-cancer treatment, (2) disease progression, (3) death, (4) withdraw of consent or lost to follow-up, (5) the end of the follow-up visit period, or (6) the end of the study, whichever occurs first. Any visits for subsequent therapy may replace protocol required survival follow-up visits. Phone follow-up is acceptable.

**Product:** Pembrolizumab

**Protocol/Amendment No.:** UVA Breast 48  
V04-13-21

j All AEs occurring within 30 days after the last dose of trial treatment will be recorded. SAEs (related and unrelated to trial treatment), UADEs and ECIs occurring up until 90 days following cessation of treatment, or 30 days following cessation of treatment if the subject initiates new anticancer therapy, whichever comes first, will be recorded. Afterwards, only SAEs, UADEs and ECIs that are related to trial treatment will be reported. The 90 day SAE collection may be collected by phone.

k Optional tumor biopsies of HIFU treated lesion and distant tumor site where clinically safe.

l Bloods for immunologic testing should be collected prior to study drug infusion and will require 4 tubes (10 ml tubes).

m Breast biopsy target is minimum of 6 core needle passes. For the cycle 2 biopsy, three of the needle passes should target the central ablated zone and three should target the peri-ablation zone.

n Survival follow-up may be completed by phone.

o Refer to [Table 6](#) for a complete list of analyses to be completed as part of the comprehensive chemistry panel.

**Product:** Pembrolizumab

**Protocol/Amendment No.:** UVA Breast 48

V04-13-21

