### 5.2.2 Dose Modification

Adverse events (both non-serious and serious) associated with pembrolizumab exposure may represent an immunologic etiology. These adverse events may occur shortly after the first dose or several months after the last dose of treatment. Pembrolizumab must be withheld for drug-related toxicities and severe or life-threatening AEs as per [Table 4](#) below. See [Section 5.6](#) for supportive care guidelines, including use of corticosteroids.

Table 4: Dose Modification and Toxicity Management Guidelines for Immune-related AEs Associated with Pembrolizumab Monotherapy and IO Combinations

General instructions:				
irAEs	Toxicity Grade (CTCAE v5.0)	Action With Pembrolizumab	Corticosteroid and/or Other Therapies	Monitoring and Follow-up

**Product:** Pembrolizumab

**Protocol/Amendment No.:** UVA Breast 48

V04-13-21

Pneumonitis	Grade 2	Withhold	

Administer corticosteroids (initial dose of 1 to 2 mg/kg prednisone or equivalent) followed by taper

Add prophylactic antibiotics for opportunistic infections

	

Monitor participants for signs and symptoms of pneumonitis

Evaluate participants with suspected pneumonitis with radiographic imaging and initiate corticosteroid treatment

	Recurrent Grade 2, Grade 3 or 4	Permanently discontinue		
Diarrhea/Colitis	Grade 2 or 3	Withhold	

Administer corticosteroids (initial dose of 1 to 2 mg/kg prednisone or equivalent) followed by taper

	

Monitor participants for signs and symptoms of enterocolitis (ie, diarrhea, abdominal pain, blood or mucus in stool with or without fever) and of bowel perforation (ie, peritoneal signs and ileus)

Participants with <math>\geq</math>Grade 2 diarrhea suspecting colitis should consider GI consultation and performing endoscopy to rule out colitis

Participants with diarrhea/colitis should be advised to drink liberal quantities of clear fluids. If sufficient oral fluid intake is not feasible, fluid and electrolytes should be substituted via IV infusion

	Recurrent Grade 3 or Grade 4	Permanently discontinue		

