##### **5.5.2 Prohibited Concomitant Medications**

Subjects are prohibited from receiving the following therapies during the Screening and Treatment Phase (including retreatment for post-complete response relapse) of this trial:

**Product:** Pembrolizumab

**Protocol/Amendment No.:** UVA Breast 48

V04-13-21

- Antineoplastic systemic chemotherapy or biological therapy
- Immunotherapy not specified in this protocol
- Chemotherapy not specified in this protocol
- Investigational agents other than pembrolizumab
- Radiation therapy
  - Note: Radiation therapy to a symptomatic solitary lesion or to the brain may be allowed at the investigator's discretion.
- Live vaccines within 30 days prior to the first dose of trial treatment and while participating in the trial. Examples of live vaccines include, but are not limited to, the following: measles, mumps, rubella, varicella/zoster, yellow fever, rabies, BCG, and typhoid vaccine.
- Systemic glucocorticoids for any purpose other than to modulate symptoms from an event of clinical interest of suspected immunologic etiology. The use of physiologic doses of corticosteroids may be approved after consultation with the Sponsor.

Subjects who, in the assessment by the investigator, require the use of any of the aforementioned treatments for clinical management (except glucocorticoids for irAE's) should be removed from the trial. Subjects may receive other medications that the investigator deems to be medically necessary.

The Exclusion Criteria describes other medications which are prohibited in this trial.

There are no prohibited therapies during the Post-Treatment Follow-up Phase.

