## 7.2 Assessing and Recording Adverse Events

### 7.2.1 Time Span for Recording Adverse Events

All adverse events that occur after the consent form is signed but before treatment allocation/randomization must be reported by the investigator if they cause the subject to be excluded from the trial, or are the result of a protocol-specified intervention, including but not limited to washout or discontinuation of usual therapy, diet, placebo treatment or a procedure.

From the time of treatment allocation/randomization through 30 days following cessation of treatment, all adverse events must be reported by the investigator. Such events will be recorded at each examination on the Adverse Event case report forms/worksheets. The reporting timeframe for adverse events meeting any serious criteria is described in [Section 7.2.6](#). The investigator will make every attempt to follow all subjects with non-serious adverse events for outcome.

Adverse events will not be collected for subjects during the pre-screening period (for determination of archival tissue status) as long as that subject has not undergone any protocol-specified procedure or intervention. If the subject requires a blood draw, fresh tumor biopsy etc., the subject is first required to provide consent to the main study and AEs will be captured according to guidelines for standard AE reporting.

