#### **7.2.6.1 Events of Clinical Interest**

Selected non-serious and serious adverse events are also known as Events of Clinical Interest (ECI) and must be reported within 24 hours to the Sponsor and within 2 working days to Merck Global Safety. (Attn: Worldwide Product Safety; [contact]).

For the time period beginning when the consent form is signed until treatment allocation/randomization, any ECI, or follow up to an ECI, that occurs to any subject must be reported within 24 hours to the Sponsor and within 2 working days to Merck Global Safety if it causes the subject to be excluded from the trial, or is the result of a protocol-specified intervention, including but not limited to washout or discontinuation of usual therapy, diet, placebo treatment or a procedure.

For the time period beginning at treatment allocation/randomization through 90 days following cessation of treatment, or 30 days following cessation of treatment if the subject initiates new anticancer therapy, whichever is earlier, any ECI, or follow up to an ECI, whether or not related to Merck product, must be reported within 24 hours to the Sponsor and within 24 hours to Merck Global Safety.

Events of clinical interest for this trial include:

1. an overdose of Merck product, as defined in [Section 7.2.3](#) - Definition of an Overdose for This Protocol and Reporting of Overdose to the Sponsor, that is not associated with clinical symptoms or abnormal laboratory results.
2. an elevated AST or ALT lab value that is greater than or equal to 3X the upper limit of normal and an elevated total bilirubin lab value that is greater than or equal to 2X the upper limit of normal and, at the same time, an alkaline phosphatase lab value that is less than 2X the upper limit of normal, as determined by way of protocol-specified laboratory testing or unscheduled laboratory testing.\*

**\*Note:** These criteria are based upon available regulatory guidance documents. The purpose of the criteria is to specify a threshold of abnormal hepatic tests that may require an additional evaluation for an underlying etiology.

**Product:** Pembrolizumab

**Protocol/Amendment No.:** UVA Breast 48

V04-13-21

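### New non-serious immune-related events that start more than 30 days after the last dose go unrecorded unless they are listed ECIs, although section 5.2.2 expects onset up to several months later

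*Combined protocol and SAP*

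**What the plan says.** The protocol uses two tiers of safety collection after treatment.

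- **All adverse events, to 30 days.** Footnote j of the flow charts for both arms reads "All AEs occurring within 30 days after the last dose of trial treatment will be recorded". Section 7.2.1 agrees: "From the time of treatment allocation/randomization through 30 days following cessation of treatment, all adverse events must be reported by the investigator". Section 5.8 and footnote h of the second-course chart give the same limit. Table 9 sets database deadlines only for events inside it.
- **Selected events, to 90 days.** The same footnote extends collection for "SAEs (related and unrelated to trial treatment), UADEs and ECIs occurring up until 90 days following cessation of treatment", shortened to 30 days if new anticancer therapy starts. It then adds: "Afterwards, only SAEs, UADEs and ECIs that are related to trial treatment will be reported". UADEs are unanticipated adverse device effects.

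On timing of the drug's immune toxicity, section 5.2.2 first says that pembrolizumab-associated events of both kinds, non-serious and serious, may be immunologic. It continues: "These adverse events may occur shortly after the first dose or several months after the last dose of treatment".

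The sections differ on whether immune events are ECIs. Section 5.5.2 allows systemic glucocorticoids to manage symptoms from "an event of clinical interest of suspected immunologic etiology". Section 7.2.6.1 opens its list with "Events of clinical interest for this trial include" and gives two items: an overdose without symptoms or abnormal laboratory results, and a defined combination of transaminase, bilirubin and alkaline phosphatase values.

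**The concern.** The protocol names a late harm and says it can be non-serious, but gives no rule for recording a new non-serious case once 30 days have passed. The ECI category could fill the gap, and 5.5.2 reads as if it does. The list in 7.2.6.1 does not bear that out.

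Section 3.2 makes the adverse event profile of the combination the only secondary objective, with the hypothesis that it will resemble the profiles already reported for each modality. Section 4.4 calls this the first human study of the combination. If the documents are followed as written, the profile is incomplete for late non-serious immune events. Sites reading 5.5.2 and 7.2.6.1 differently could also record the same event differently.

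There is little indirect trace either. Section 5.5.1 records concomitant medication beyond 30 days only in connection with SAEs and ECIs, so steroids given for such an event would not appear.

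**Working it through.** The plan gives no observation-time figure to reproduce. The check compares the rules by event type, then does simple calendar arithmetic.

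**1. What happens to each type of event after the last dose, when no new anticancer therapy starts**

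| Event | Rule | Source |
|---|---|---|
| Serious, including important medical events | To 90 days; later if related | 6.1 footnote j, 7.2.6, Table 7 |
| UADE | To 90 days; later if related | 6.1 footnote j |
| Listed ECI (symptom-free overdose; hepatic pattern) | To 90 days; later if related | 6.1 footnote j, 7.2.6.1 |
| Grade >1 event arising by the 30-day safety visit | Followed to Grade 0–1 or new therapy | 7.1.6.3.1 |
| New, non-serious, not a listed ECI | To 30 days; no rule after that | 6.1 footnote j, 5.8, 7.2.1 |

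Only the last row has a gap.

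**2. Does the ECI list close it?** The hepatic item needs AST or ALT ≥3 × ULN, bilirubin ≥2 × ULN and alkaline phosphatase <2 × ULN together.
- A non-serious Grade 2 skin event meets neither listed item.
- A non-serious symptomatic thyroid event meets neither.
- A non-serious transaminase rise with normal bilirubin fails the bilirubin condition.

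On the wording of 5.5.2 all three might count as ECIs. On the list in 7.2.6.1 none does.

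**3. Length of the uncovered period.** Take a last dose on day 64 (section 2.1, both arms).
- General recording ends on day 64 + 30 = 94.
- The SAE/ECI window ends on day 64 + 90 = 154.
- Difference: 154 − 94 = 60 days, the same in both arms because both windows run from the last dose.

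For a participant who starts new therapy the longer window also falls back to 30 days, so nothing is gained.

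**4. Weight of one event.** Section 8.2 targets 12 participants, 6 per arm, and summarises events by arm and overall. One participant with an unrecorded event is 1/12 = 8.3 percentage points overall and 1/6 = 16.7 points within an arm. At the maximum accrual of 15 it is 1/15 = 6.7 points overall.

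**5. Are there contacts at which to record it?** Both flow charts mark an adverse event review at the 12-week follow-up, and footnote j allows the 90-day SAE collection by phone. If the 12 weeks run from the last dose, the visit is due at 12 × 7 = 84 days. With the chart's ±3 weeks it falls between 84 − 21 = 63 and 84 + 21 = 105 days, so it can miss the end of the window. The 90-day contact reaches it.

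**The case against.** The strongest reply is that this is a deliberate two-tier scheme, applied consistently in 5.5.1, 5.8, 6.1, 7.2.1 and 7.2.6, and that the sentence in 5.2.2 is a dose-modification caution, not a collection rule. The consistency is real. But 5.2.2 is still the protocol's own account of when these events occur, and the collection rules do not follow it for non-serious ones.

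Second, much late toxicity is already caught: serious events, non-hospitalised events judged medically important, and the hepatic ECI. Sections 7.2.10 and 7.2.11.1 also require dose-limiting toxicities to be entered within 5 days of the team learning of them, with no 30-day limit stated. This stands and narrows the gap. The dose-limiting route is uncertain, because the definition turns on permanent discontinuation and its meaning after dosing has ended is unclear.

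Third, the list in 7.2.6.1 is introduced in open terms, so 5.5.2 may already bring immune events under the 90-day window. If that is the intention, the remedy is to say so.

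Fourth, the existing contacts are imperfect. Footnote i lets follow-up visits stop at progression, and 7.1.6.4.1 then leaves annual telephone contact for survival, so many participants may have only the 90-day call. The main-course charts show no thyroid tests after the treatment cycles and no chemistry after the 30-day safety visit. A call will not find silent thyroid or liver events. This stands as a limit on the remedy.

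Fifth, the earlier profiles named in 3.2 may have used a 30-day window, in which case a longer one would upset a like-for-like comparison. The documents do not give those windows. Reporting both counts answers the point.

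**Conclusion.** The point holds in a limited form. New non-serious immune-related events that are not listed ECIs and begin more than 30 days after the last dose are not recorded, against the expectation set in 5.2.2, and 5.5.2 and 7.2.6.1 disagree on whether such events are ECIs. Applying the existing window would add 60 days for participants who start no new therapy. This affects the completeness of a descriptive profile in about 12 people; it does not touch the primary endpoint. It rests on reading the 7.2.6.1 list as complete.

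Three stronger readings are not supported:

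- **Delayed immune toxicity is never reported.** A reader might infer this from the 30-day rule alone. Serious events, important medical events and the hepatic ECI are collected to 90 days, and related ones afterwards.
- **The cut-off shortchanges Arm A.** For a day-64 last dose, recording ends 94 − 22 = 72 days after first pembrolizumab in Arm A and 94 − 1 = 93 days in Arm B. Those 21 days come from Arm A's later start. Under a 90-day window they remain (154 − 22 = 132 against 154 − 1 = 153). Observation from HIFU is equal (94 − 15 = 79 in each arm), and 8.2 plans no definitive comparison between arms.
- **A known share of events is lost, so the combination looks safer than it is.** The documents give no onset distribution, so no share can be calculated. Without the collection windows behind the earlier profiles, the direction of any bias in the 3.2 comparison is unknown.

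**What to change.** 1. Reconcile 5.5.2 with 7.2.6.1 by stating whether immune-related events are ECIs in this trial.
2. In footnote j (both arms), second-course footnote h and section 7.2.1, or through the ECI list, state that immune-related events of the types in Table 4, serious or not, are recorded under the existing SAE/ECI window: 90 days after the last dose, or 30 days if new anticancer therapy starts. Align 5.8 and, if the ECI route is not used, the concomitant medication rule in 5.5.1.
3. Collect them at the 90-day SAE contact or the 12-week follow-up adverse event review. Keep 30 days for all other non-serious events.
4. In 8.2, report counts to 30 days and to 90 days separately, so that comparison with earlier profiles stays possible.

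The change concerns data capture only and alters no treatment rule. It costs footnote and case report form wording, a few more events to record, and slightly higher reported immune-event rates. Because no tests are added, events visible only in the laboratory may still be missed, and the report should say so. The ECI route carries an extra burden: 7.2.6.1 requires every ECI to reach the sponsor within 24 hours, which would then apply to non-serious immune events throughout the trial. The footnote route avoids this.
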